**6. Participant Exclusion Criteria:**

Selection will be consistent with current standard of care. Any patient that is not a suitable candidate for LASIK will not be included.

**7. Is a substantial percentage of the participant population anticipated to be non-English speaking?** Yes  No

IRB\_00074858

Created: 6/23/2014 8:21 PM

IRB\_00074858

PI: [name]

Submitted: 7/28/2014

View: 4. Study Information

**Title:** 70 versus 110 Degrees Side-cut Angles in Femtosecond  
Laser-assisted in situ Keratomileusis

## 4. Study Information

**1. Design of Study (select all that apply):** **Non-Experimental and/or Descriptive Research Design:**

There are no items to display

 **Experimental and/or Interventional Research Design:**

Prospective Biomedical Intervention or Experiment  
Randomized Trial

 **Development of a research resource (repositories, databases, etc.)** **Other****2. Does your study involve the use of any placebo?** Yes  No**3. Length of entire study, from initiation through closeout:**

2 years

**4. How will participants be recruited or identified for inclusion in the study?****a. Select all methods that will be used:**

In-person contact (e.g., patients, students, etc.)

Written advertising (flyers, brochures, website postings, newspaper ads, etc.)

Other

Information will be included on the moran eye center website, moran eye center facebook, and moran eye center twitter account.

[http://healthcare.utah.edu/moran/patient\\_care/refractive\\_surgery\\_lasik/](http://healthcare.utah.edu/moran/patient_care/refractive_surgery_lasik/)

<https://www.facebook.com/moraneyecenter>

<https://twitter.com/MoranEyeCenter>

**b. Describe the recruitment/participant identification process in detail (e.g. who will review charts or records, who can refer participants to the study, where will flyers be posted, how often will recruitment letters be sent, when will follow-up phone calls be made, etc.):**

When patients come in requesting refractive surgery, they are asked if they would like to participate in the study. An advertisement will be included on the Moran Eye Center website, facebook page, and twitter account, as well as in newsprint.

**5. How will consent be obtained?**

Informed Consent Process (with or without a document)

**6. Describe all the procedures chronologically, from screening/enrollment through study closeout, which will be completed in the research project.**

Patients who are interested and eligible to participate in this study will sign the study informed consent prior to surgery. As is standard for our LASIK cases, they will also be required to watch an informational video, read and sign the "Consent to Have Refractive Surgery" and respond to a brief test concerning its content.

All surgical procedures will be performed according to the surgeons' standard practices. The study outcome measures are standard of care for pre-operative and post-operative evaluation of refractive surgery patients.

All study outcome measures will be evaluated for both eyes at every visit. Patient will be masked as to the treatment they receive in either eye so as not to influence their subjective responses and visual measurements. Post-operative evaluations will be performed at 1 day, 1 week ( $\pm$  3 days), 1 month ( $\pm$  10 days), 3 months ( $\pm$  14 days), 6 months ( $\pm$  1 month), and 12 months ( $\pm$  1 month). Interim examinations may be performed as necessary according to the surgeon's usual care, but are not considered part of the study data.

Patients will be discontinued from the study if, on the day of surgery, both eyes cannot be randomized and operated as per protocol. Patients have the right to withdraw at any time and future medical care will not be influenced by their lack of participation.

Patients will be evaluated with the following procedures:

- Manifest refraction (sphere, cylinder and axis): Pre op and post-op months 1 ( $\pm$  10 days), 3 ( $\pm$  14 days), 6 ( $\pm$  1 month), and 12 ( $\pm$  1 month).
- Uncorrected corrected visual acuity: Pre-op and post-op day 1, week 1, and months 1 ( $\pm$  10 days), 3 ( $\pm$  14 days), 6 ( $\pm$  1 month), and 12 ( $\pm$  1 month) using the Snellen Eye chart
- Best corrected visual acuity: Pre-op and post-op months 3 ( $\pm$  14 days), 6 ( $\pm$  1 month), and 12 ( $\pm$  1 month).
- Pupil size measured in the dark: Pre-op only

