**6. Study Purposes and Objectives:**

Different side-cut angles have been used in Femtosecond Laser-assisted in Situ Keratomileusis (FS-LASIK), but no study has compared the safety and efficacy of 70 and 110 degrees side-cut angles. We aim to conduct a prospective trial comparing 70 and 110 degrees side-cut angles on same patient undergoing FS-LASIK. One angle will be performed on the right eye and the other on the left eye. The study will evaluate uncorrected visual acuity, best corrected visual acuity, intraoperative, and postoperative complications. By performing different side-cut angles on a same individual will allow a direct comparison of outcomes, minimizing confounding variables. Additionally, the LASIK flap will be performed using either the Abbott Medical Optics Intralase femtosecond laser or the Alcon Wavelight FS200 femtosecond laser.

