**8. Is there a safety monitoring plan for this study?**

Yes  No

**9. Provide a summary of the statistical methods, data analysis, or data interpretation planned for this study. Factors for determining the proposed sample size (e.g., power) should be stated.**

Summary statistics will be calculated and used to describe the treatment groups (70 versus 110 degrees side-cut angles) in terms of all study variables: manifest refraction, corrected and uncorrected visual acuity and LASIK system used (FS200 or intralase). Statistics will be compiled for the one week, one month, three month, six month and 12 month time points post operatively. Paired t-tests will be used to analyze the difference of corrected and uncorrected visual acuity obtained by each group at the post-op time points, as well as the average change from pre-op to post op corrected and corrected visual acuities. In order to provide a statistically significant beta values, a N number of 200 patients will be needed.

IRB\_00074858

Created: 6/23/2014 8:21 PM

IRB\_00074858

PI: [name]

Submitted: 7/28/2014

View: 4.2 Consent Process

**Title:** 70 versus 110 Degrees Side-cut Angles in Femtosecond  
Laser-assisted in situ Keratomileusis

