## 8. Resources and Responsibilities

### 1. \* State and justify the qualifications of the study staff:

[name] specializes in the medical and surgical treatment of corneal and anterior segment eye diseases. His expertise includes all types of corneal transplantation, cataract surgery, and vision correction using lasers, intra-ocular lenses, and conductive keratoplasty.

Sub-investigators are ophthalmology fellows (M.D.s) and will work under the supervision of [name].

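### The plan masks the patient but does not withhold the eye-by-angle assignment from whoever refracts and scores acuity, so an examiner preference could enter the within-patient difference

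*Combined protocol and SAP*

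**What the plan says.** Masking appears once, in 4. Study Information, item 6 (procedures): "Patient will be masked as to the treatment they receive in either eye so as not to influence their subjective responses and visual measurements". Nothing is said there or elsewhere about masking the refractionist, the acuity examiner, the surgeon or the analyst, or about where the assignment is recorded and who can see it.

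The same item describes the measurements without naming who takes them. "All study outcome measures will be evaluated for both eyes at every visit". "The study outcome measures are standard of care for pre-operative and post-operative evaluation of refractive surgery patients". The listed outcomes include "Manifest refraction (sphere, cylinder and axis): Pre op and post-op months 1" and onward to month 12, uncorrected acuity taken "using the Snellen Eye chart", and best corrected acuity. No scoring, prompting or stopping rule is given for the chart.

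The comparison is within the patient: "One angle will be performed on the right eye and the other on the left eye" (Study Purposes and Objectives). Under 4. Study Information, item 9, "Paired t-tests will be used to analyze the difference of corrected and uncorrected visual acuity obtained by each group at the post-op time points". The sample size is 200 patients; alpha, power, effect size and SD are not stated.

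**The concern.** The masking sentence gives its own reason: knowledge of the treatment could alter subjective responses and measured vision. That reason applies to both people in the examination. Manifest refraction is an exchange between patient and examiner, and a chart reading depends on how much the examiner encourages, when the test stops and which response is accepted. Best corrected acuity inherits whatever refraction endpoint was chosen. The plan closes the patient's route and leaves the examiner's route unaddressed.

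At stake is the trial's main strength. Comparing the two eyes of one patient removes patient-level confounding, but a tendency to favour one angle acts on the difference between the eyes, which is the quantity being tested.

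**Working it through.** **No plan figure to reproduce.** The plan gives no figure on masking or measurement bias. Its sample size of 200 cannot be reproduced either, because its inputs are not stated. The check is therefore a structural argument plus an illustration on assumed values.

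**Step 1: what the design removes.** For patient i, write the acuity difference (110-degree eye minus 70-degree eye) as

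D_i = δ + β + γ·s_i + e_i

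Here δ is the true angle effect, β a systematic examiner shift tied to the angle, γ a right-left effect with s_i = +1 or −1 by eye assignment, and e_i random error.

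- Pairing cancels anything common to both eyes before D_i is formed. It does not touch β.
- Randomizing eyes makes s_i average to zero, so γ drops out. β follows the angle and not the side, so it stays.
- The mean of D_i estimates δ + β at any sample size. A larger sample shrinks only the standard error.

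**Step 2: illustration of sensitivity.** Inputs:

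- n = 200 pairs, from the plan; all taken as complete (assumption).
- Two-sided alpha 0.05 (assumption; not stated).
- Acuity analysed in logMAR (assumption; the plan names a Snellen chart and gives no conversion).
- SD of the paired difference 0.10 logMAR, range 0.08 to 0.15 (assumption; not in the documents).
- δ = 0 and β = 0.01 logMAR (hypothetical). This is half a letter if a letter is scored as 0.02 logMAR.

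Normal approximation: λ = β × √n / SD, with √200 = 14.14. The chance of p<0.05 is P(Z > 1.96 − λ) + P(Z < −1.96 − λ).

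| SD | λ | 1.96 − λ | Chance of p<0.05 |
|---|---|---|---|
| 0.08 | 0.01 × 14.14 / 0.08 = 1.77 | 0.19 | 42% |
| 0.10 | 0.01 × 14.14 / 0.10 = 1.41 | 0.55 | 29% |
| 0.15 | 0.01 × 14.14 / 0.15 = 0.94 | 1.02 | 16% |

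The noncentral t for a paired t-test with 199 degrees of freedom agrees: 29.1% at SD 0.10 and 15.5% at SD 0.15. With a smaller shift of 0.005 at SD 0.10 it gives 10.8%.

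**Step 3: does more data help?** Keep SD 0.10 and β = 0.01 and double n to 400. Then λ = 0.01 × 20 / 0.10 = 2.00, and P(Z > −0.04) is about 52%. More pairs make a false finding more likely.

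**The case against.** The strongest reply is that silence is not evidence. A reader might infer that examiners are unmasked, that a single examiner measures both eyes, or that the surgeon or the fellows take the readings. The documents support none of these. Item 6 names no examiner. The staff section (8. Resources and Responsibilities) covers qualifications and supervision, not who measures or who sees the assignment. This part of the reply stands, and the point is limited to the absence of any provision.

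Second, the size is hypothetical. A shift needs a consistent direction across patients, and the plan names no favoured angle; it says the two angles have not been compared. The Background does describe laser settings, including the side-cut angle, as matters of surgeon preference, so preferences are plausible. That does not show that any examiner holds one, or which way. A reader might take 29% as the trial's expected false-positive rate. It is not: it shows only how the test responds if a shift of that size existed.

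Third, patient masking already protects in part, because both measurements rely heavily on the patient's responses. That is fair; only the examiner's contribution is open.

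Fourth, if the operating surgeon takes the readings, a charting rule cannot mask them. That also stands, and the fix is made conditional on it. None of this removes the gap: the plan's own rationale reaches the examiner and its procedure does not.

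**Conclusion.** The point holds as a gap in protection, not as a demonstrated bias. The plan recognises that knowledge of treatment can influence visual measurements, masks the patient, and provides nothing to keep the assignment from the person who refracts and scores acuity. Any preference tied to the angle would enter the paired difference in full.

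Neither the direction nor the size of such a preference can be known from the documents. The 29% figure (range 16% to 42%) rests on the assumed SD, 200 complete pairs, logMAR scoring and a hypothetical 0.01 logMAR shift. The change is worth making because it costs little, not because the results are shown to be wrong.

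**What to change.** Extend the masking sentence in 4. Study Information, item 6, to say that:

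1. The eye-by-angle assignment is held in the randomization log and operative record and does not appear on the form used for study acuity and refraction.
2. Where existing staff other than the operating surgeon take these readings, they do not consult the assignment, and they record their results before the surgeon examines the eyes.
3. One field at each visit records whether the examiner was aware of the assignment.

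Add to item 9 that the number of readings taken by aware examiners will be reported, with a sensitivity analysis excluding them.

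Cost: a charting rule, one data field and one extra analysis. No added assessor is needed where staff other than the operating surgeon already take the readings; the documents do not say whether they do. Downside: masking is not possible when the operating surgeon takes the reading. The field would show how often that happened, and the limitation could then be reported.

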**7. Is this a multi-site study, where more than one site needs IRB approval?** Yes  No**8. Background and Introduction:**

Laser-assisted in Situ Keratomileusis has become the preferred corneal procedure to correct certain refractive errors. Technological advances have increased the accuracy and precision of current treatments. One of the major advancements in LASIK has been the introduction of Femtosecond Laser technology for flap creation. Several studies have compared microkeratome and femtosecond laser technology, showing superior accuracy and precision of flap dimensions in the latter.

The Femtosecond Laser technology provides different parameters and settings that can be changed according to the surgeon's preference. One of such parameters is the side-cut angle. Some of the most common side-cut angles used today include 45, 70, 90, and 110 degrees. Previous studies have reported on the visual outcomes of side-cut angles, but head to head comparisons are lacking. Currently, there are no studies comparing the safety and efficacy of the 70 and 110 side-cut angles in FS-LASIK. Information regarding the outcomes and complication rates between these side-cut angles will provide an objective measure that can be used when deciding which one is more suitable in FS-LASIK.

IRB\_00074858

Created: 6/23/2014 8:21 PM

IRB\_00074858

View: 2. Location and Sponsor

PI: [name]

Submitted: 7/28/2014

**Title:** 70 versus 110 Degrees Side-cut Angles in Femtosecond Laser-assisted in situ Keratomileusis

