**2. Describe the potential benefits to society AND to participants (do not include compensation):**

Evaluation of vision and complications on an individual patient who has undergone 70 degrees side-angle cut in one eye and 110 degrees side-angle cut in the other will afford a greater understanding of the safety and efficacy of using this two common side-cut angulations. There is no direct benefit to participants.

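### The day-of-surgery discontinuation rule can be read to remove patients after their angle is assigned, and the analysis summary gives their intraoperative failures no stated route into the comparison of angles

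*Combined protocol and SAP*

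**What the plan says.** Section 4, item 6 (procedures) sets the rule: "Patients will be discontinued from the study if, on the day of surgery, both eyes cannot be randomized and operated as per protocol". The same item starts the post-operative schedule the day after surgery ("Post-operative evaluations will be performed at 1 day, 1 week") and lists refraction, the acuities and pupil size. It lists no intraoperative record, and it places unscheduled examinations outside the study data.

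The safety question is stated elsewhere in the same document:

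- Section 6 of the opening form (purposes and objectives): "The study will evaluate uncorrected visual acuity, best corrected visual acuity, intraoperative, and postoperative complications".
- Background and Introduction: "Information regarding the outcomes and complication rates between these side-cut angles will provide an objective measure", offered as a basis for choosing an angle.
- Risks and Benefits, item 2, names the same pair of outcomes: "Evaluation of vision and complications on an individual patient who has undergone 70 degrees side-angle cut in one eye and 110 degrees side-angle cut".

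Section 4, item 9 (statistical methods) describes the groups by "all study variables: manifest refraction, corrected and uncorrected visual acuity and LASIK system used (FS200 or intralase". On timing it says: "Statistics will be compiled for the one week, one month, three month, six month and 12 month time points post operatively". The only planned tests are paired t-tests on visual acuity. No intention-to-treat, all-randomised or safety set is defined.

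**The concern.** The rule joins two conditions. A patient who cannot be randomised is lost before either angle can have had any effect, and the loss does no harm to the comparison. A patient whose surgery cannot be completed after the angle is assigned is different, because the reason may be the angle itself. The plan does not date the assignment, so the two groups cannot be separated.

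Case-stopping failures are among the events most relevant to a safety comparison of flap side-cut angles. If patients discontinued for them are not carried into the report, a reader cannot see how many there were, under which angle, or why. What is at stake is complete safety reporting.

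**Working it through.** **Does the plan give a discontinued patient a place in the report?**

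| Part of the plan | What it provides | Does it hold a case stopped on the day of surgery? |
|---|---|---|
| Objectives | Intraoperative complications named | Named, but with no definition, time point or population |
| Item 6, procedures | Refraction, acuities, pupil size; visits from day 1 | No intraoperative record listed |
| Item 9, variables | Refraction, acuities, laser system | No complication variable listed |
| Item 9, time points | One week to 12 months | Earlier than the first listed point |
| Item 9, tests | Paired t-tests on acuity | Need both eyes of a patient |
| Analysis sets | None defined | Not addressed |

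The outcome is named, but no stated step brings these cases into the comparison.

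**The plan's own figure.** Item 9 gives 200 patients without alpha, power, effect size or standard deviation, so that number cannot be reproduced. It is used below only as the number enrolled.

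**How many patients?** The documents give no failure rate, so every rate here is an assumption, and failures in the two eyes are taken as independent. With per-eye rates f1 and f2:

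- expected affected patients = 200 × [1 − (1 − f1)(1 − f2)]
- chance of at least one = 1 − [(1 − f1)(1 − f2)]^200

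| Assumed case-stopping failure rate | Expected patients of 200 | Chance of at least one |
|---|---|---|
| 0.1% per patient (about 0.05% per eye) | 0.20 | 18% |
| 0.25% in each eye | 1.00 | 63% |
| 0.5% in each eye | 1.99 | 87% |
| 2% v 0.5% | 4.98 | 99.4% |
| 2% v 1% | 5.96 | 99.8% |
| 3% v 1% | 7.94 | over 99.9% |

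For 2% v 0.5%: 1 − 0.98 × 0.995 = 0.0249, and 200 × 0.0249 = 4.98.

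**What the report would show.** Take 2% v 0.5%, towards the upper end of the range. Suppose that the higher-rate angle is always cut first and that a first-eye failure stops the case. About 200 × 0.02 = 4 failures occur under the first angle, leaving 200 − 4 = 196 second eyes treated, and 196 × 0.005 ≈ 1 failure under the other. Exact (Clopper-Pearson) 95% intervals:

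- Kept: 4/200 = 2.0% (0.5% to 5.0%) v 1/196 = 0.5% (0.01% to 2.8%).
- Left out: 200 − 5 = 195 patients, so 0/195 for each angle (upper limit 1 − 0.025^(1/195) = 1.9%).

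With the higher-rate angle cut second, the kept counts are 4/199 v 1/200. The kept intervals overlap widely, so they would not establish a difference. No paired p-value is given: when a first-eye failure stops the case, the second eye is untreated and the pair is incomplete.

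**Effect on the acuity test.** Assume a two-sided 5% level and 80% power with 200 pairs. The detectable difference is (1.960 + 0.842)/√200 = 0.198 standard deviations of the within-patient difference. Power with n pairs is Φ(0.198√n − 1.960): 79.0% at 195 pairs and 78.4% at 192, the largest loss in the table (200 − 8).

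**The case against.** The strongest reply is that the rule is a gate applied before surgery: a patient who turns out unfit for same-day bilateral treatment does not proceed. The wording allows this. The timing of assignment is unstated, so one can say only that the rule may reach patients already assigned.

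Second, discontinuation may simply end follow-up. Nothing orders recorded events to be deleted or calls for a safety table of completers only. This stands, and the 0/195 above is a conditional outcome. A reader might infer that the plan discards these events; the text does not support that.

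Third, item 9 is a summary and not clearly a closed list. It omits pupil size and the day-1 acuity, both collected under item 6, and it includes the laser system, which belongs to no post-operative visit. The objectives do name intraoperative complications. So absence from item 9 is weak evidence that the events would go unreported. It remains true that no section says how they are recorded, counted or analysed.

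Fourth, the wider gap is that complications are named but never given an analysis, and the discontinuation rule is a small part of it. This is fair, but adding a complication variable would not by itself settle whether discontinued patients are counted.

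Fifth, the size rests wholly on assumed rates, and a range of 0.2 to 8 patients says little about severity. At the lowest rate the likely number is none. Events handled within the surgeons' standard practice may still count as operated per protocol, which leaves only case-stopping failures.

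**Conclusion.** The point holds in a limited form. The rule can be read to exclude patients after assignment, for reasons that may depend on the angle, and the plan states no route by which their failures reach a comparison it sets out to make. The harm is conditional: safety reporting could be incomplete if these patients are not carried forward. Under the assumed rates about 0.2 to 8 of 200 patients are involved.

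Two stronger readings are not supported. A reader might infer that the rule biases or reverses the comparison of angles. An assumed split such as 6 v 0 failures (exact p = 0.031) turning into 0 v 0 in 194 patients would look that way, but those counts are chosen and nothing in the documents supports them. No biased acuity result is shown either, and the power loss is under two percentage points. A reader might also infer that safety is not monitored. The answer on a safety monitoring plan cannot be read in the available text, so nothing follows from it.

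This is a cheap improvement to a stated rule.

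**What to change.** - State in section 4, item 6 when the angle is assigned to each eye.
- Limit exclusion from the dataset to patients removed before assignment, and keep every patient with an assigned angle in the dataset for safety.
- Add intraoperative complications and uncompleted cases to the variables in item 9, with the day of surgery as a reporting point.
- Report uncompleted cases by assigned angle and reason among all randomised patients, and intraoperative events by angle among treated eyes, with exact confidence intervals. If there are none, report zero by angle. No significance test is needed. Showing eye order, or counting eyes from the start of flap creation, would help but is a reporting preference.
- Keep the paired acuity analysis on completed pairs, and state the number of incomplete pairs.
- Reconcile the objectives, the background, and items 6 and 9 of section 4.

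The change concerns data retention and reporting only; clinical handling of the eye is unaffected. It costs a few extra data fields and one more table, with no added visits or patients and no change to the acuity test. It should be settled before enrolment, because the assigned angle and the reason for stopping may not be recoverable later if they were never recorded.
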